## 9.4.3. Reporting and Follow-up of Pregnancy

Patients who become pregnant while on study must immediately discontinue study treatment, and the pregnancy must be immediately reported to the Medical Monitor. Pregnancies occurring up to 6 months after the completion of the study medication must also be reported to the Sponsor.

The investigator should inform the patient of the risks of continuing with the pregnancy and the possible effects on the fetus. Monitoring of the patient should continue until conclusion of the pregnancy.

In the event of a pregnancy occurring in the partner of a male patient participating in the study, the pregnant partner should be requested to report the pregnancy to the investigator, who in turn

should report it to the Sponsor. The partner should also be informed of the risks of continuing with the pregnancy, and the possible effects on the fetus.

#### 10. Statistical Methods

Detailed methodology for summary and statistical analyses of the data collected in this study will be documented in a Statistical Analysis Plan (SAP), which will be dated and completed prior to database lock. The SAP may modify the plans outlined in the protocol; however, any major modifications of the primary endpoint and/or its analysis will also be reflected in a protocol amendment.

#### 10.1. General Considerations

Categorical variables will be summarized by frequency distributions (number and percentage of patients) and continuous variables will be summarized by descriptive statistics (mean, standard deviation, median, minimum, maximum). Testing will be conducted using a one-sided 0.025/two-sided 0.05 significance level unless stated otherwise. Only 95% confidence intervals (CI) will be calculated when indicated. Descriptive statistics will be displayed in abbreviated treatment identifiers instead of seribantumab + fulvestrant, fulvestrant, and overall.

# 10.2. Statistical Hypothesis and Determination of Sample Size

The primary hypothesis is to test for differences in progression-free survival (PFS) distributions.

A stratified log-rank test will be used to analyze PFS differences with the stratification factors in the model: Statistical significance will be determined by using a one-sided type I error of 0.10. A stratified Cox proportional hazards model will be used to estimate the hazard ratio using geographic region (US, non-US) and bone-only disease (yes, no) as stratification factors.

The median PFS for the control arm (fulvestrant + placebo) is assumed to be 4.0 months in this patient population. A total of 58 PFS events will be required across two treatment arms randomized in a 1:1 ratio giving 80% power to detect a hazard ratio (HR)  $\leq$  0.57 (mPFS: 4 v 7), assuming a 1-sided significance level of 0.10. Approximately 200 patients will need to be screened in order to accrue 80 randomized in approximately 16 months with a total study duration of 20 months.

#### 10.3. Analysis Populations

Patients that have signed informed consent, are identified as HRG positive based on centralized tissue analysis, and have successfully completed study entry criteria will be delineated into the following analysis populations:

- **Intent-to-Treat (ITT) population**: This population includes randomized patients. Patients will be analyzed in the randomized group.
- **Per Protocol (PP)**: This population includes randomized patients. Patients will be analyzed in the randomized group. The PP population is the primary efficacy population and will only include patients that meet inclusion/exclusion criteria as defined in Section 4.1 and 4.2 and are confirmed HRG positive based on the prospective fresh centralized tissue analysis (pre-treatment tissue sample).
- Safety (SAF) population: The safety population includes patients receiving at least one dose of study medication. All safety analyses will be performed on this population.
- **PK population**: All treated patients with at least one PK assessment.

#### 10.4. Disposition, Demographics, and Baseline Characteristics

Disposition of patients will be summarized, including those screened, treated, and discontinued. Reason for discontinuation will be summarized. Demographic and baseline characteristics will be summarized. Medical history and prior medications will be tabulated.

### 10.5. Efficacy Analysis

### 10.5.1. Primary Efficacy Analysis

PFS is defined as the time from randomization to the first documented radiographical progression of disease using RECIST v1.1 or death from any cause, whichever comes first. Details of censorship will be thoroughly explained in the SAP. PFS will be analyzed based on investigator assessed. The primary endpoint will be based on the investigator assessment of disease progression.

The Kaplan-Meier estimates will be used to determine median PFS and 80% CI for each treatment group. A stratified log-rank will be used to test for PFS distribution differences. A stratified Cox proportional hazards model will be used to estimate the hazard ratio and corresponding 80% confidence intervals. Stratification factors include: Geographic region (US, non-US) and bone-only disease (yes, no).

### 10.5.2. Secondary Efficacy Analysis

Overall Survival (OS) is defined as the time from the date of randomization to the date of death from any cause. Patients who are alive or lost to follow-up at the time of the analysis will be censored at the last known alive date. The majority of patients are expected to live at least 2 years, therefore the proportion of deaths at the time of the PFS analysis will not be sufficient for formal hypothesis testing of OS at that time.

Various sensitivity analyses will be performed on PFS and OS which will be further detailed in the SAP. PFS and OS will also be analyzed as an unstratified log-rank test for the primary and all sensitivity analysis as well. Other analyses include a PFS sensitivity analysis performed by declaring all censors as events and testing with a stratified log-rank.

Objective Response Rate (ORR) is defined as the proportion of patients with a RECIST v1.1 response recorded from randomization until disease progression characterized as either a Complete Response (CR) or Partial Response (PR) relative to the total number of evaluable patients. Frequency and percent will be as descriptive statistics while a Cochran-Mantel-Haenszel (CMH) test stratified by stratification factor will be tested. A chi-square test without stratification will also be presented. Frequency and percent along with 95% CI will be calculated

Time to Progression (TTP) is defined as the time from the date of randomization to the date of objective tumor progression. Those patients without objective tumor progression will be censored at the date of last tumor assessment documenting no objective progression. Patients who died prior to first scan will be censored on the date of death.

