#### 4.4. Patient Discontinuation

A patient may withdraw from the study at any time and for any reason. It is intended that patients will be treated until investigator-determined progressive disease (radiologic or clinical deterioration) or unacceptable toxicity. Some possible reasons for withdrawal from treatment include, but are not limited to the following:

- Progressive neoplastic disease per RECIST v1.1
- Clinical deterioration
- Adverse event, including treatment being withheld for 21 consecutive days without resolution of toxicities to grade 1 or baseline value

- Protocol violation / non-compliance
- Withdrawal of consent
- Investigator or sponsor decision
- Patient is lost to follow-up

When a patient is discontinued from treatment for any reason, they are to undergo the assessments in the End of Treatment visit within 30 days of the last dose. All patients who discontinue treatment as a result of an adverse event must be followed until resolution or stabilization of the adverse event. At the time a patient withdraws from study treatment, an attempt should be made to determine the reason(s) for discontinuation. The patient will continue to be followed for survival information every 2 months after completion of the End of Treatment visit. All patients, including patients who discontinue treatment for reasons other than progressive disease per RECIST 1.1, should undergo a scan to assess disease status at the time of treatment discontinuation, and again 8 weeks following treatment termination.

If a patient does not return to the clinic for the end of treatment visit or is not reached for overall survival follow-up, at least 3 documented attempts, including one via certified mail, should be made to contact the patient. If there is no response to these requests, the date of death should be captured from public records.

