-  Seribantumab PK: all patients; in relation to seribantumab infusion
  - a C1W1: immediately after the end of the Seribantumab infusion (+15 mins)
  - b C1W3, C2W1, C2W3: pre-dose
-  Immunogenicity samples should be collected for all patients prior to dosing.
-  In the event a patient experiences an infusion reaction at any point in the study, an anti-Seribantumab antibody assay will be taken within 24 hours of the event, in addition to the scheduled time-points. For patients who experience a Grade 3 or 4 infusion reaction to Seribantumab, an anti-Seribantumab antibody titer will be taken as close to the onset of the infusion reaction as possible, at the resolution of the event and 28 days (+/- 2 days) following the event.
-  Disease evaluation per RECIST version 1.1.
-  Tumor sample is to be collected for all HRG positive patients that receive HRG results for eligibility based on testing of archived samples. An additional sample is not required for patients who underwent a fresh biopsy for eligibility testing.
-  Fulvestrant PK: all patients: prior to seribantumab injection
-  Serum for biomarkers should be collected pre-infusion on week 1 of each cycle for all patients
-  End of treatment (30-day Follow-up) visit should be completed within 30 days of the last dose of study drug
-  Should patients refuse or drop out of survival follow-up, attempts should be made to obtain any death information available via public records.
-  One reading prior to infusion with seribantumab.
-  AE/SAE collection to be included. S/AE assessment and reporting will proceed as outlined in Sections 9.2 and 9.3
-  All patient hospitalizations and/or hospital visits should be collected, whether or not associated with an adverse event.
-  In addition to the timepoints noted, MUGA or Echocardiogram should be performed post-screening for any study patient who develops symptoms consistent with new onset of congestive heart failure.
-  Unless performed within the last 4 weeks as part of assessments in the previous cycle
-  Sample to be collected prior to any study treatment.

Proprietary and Confidential Page 44 of 65

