## 6.6. Survival Follow-up

Survival data will be collected via telephone or clinic visits every 2 months (±10 days) from the date of the 30-day follow-up visit until death, loss to follow-up, withdrawal of consent, or study termination by the Sponsor. In addition, any new anti-cancer therapies and procedures should be collected and documented. All survival information will be captured using the electronic data capture (EDC) system. Should patients refuse or drop out of survival follow-up, attempts should be made to obtain any death information via public records whenever possible.

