## 3.2 Overall Survival

Overall Survival (OS) is defined as the time from randomization to the date of death for any cause. In the absence of confirmation of death, survival time will be censored at the last date the patient is known to be alive. Length of OS will be calculated in days and reported in months.

[Death/Censor Date - Randomization Date + 1] / 30.4375.

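### Record searches for patients lost to survival follow-up supply deaths but no alive dates, so on the natural reading OS curves are biased downward and the OS hazard ratio shifts against the arm with more loss

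*Protocol*

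**What the plan says.** Two sets of instructions meet here.

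**Collecting survival status.** Protocol 6.6: "Survival data will be collected via telephone or clinic visits every 2 months (±10 days) from the date of the 30-day follow-up visit". When contact fails, records are searched for deaths:
- Protocol 4.4, after at least three documented attempts at contact: "If there is no response to these requests, the date of death should be captured from public records".
- Protocol 6.6: "Should patients refuse or drop out of survival follow-up, attempts should be made to obtain any death information via public records whenever possible".
- Protocol 6.1, footnote 15 to the schedule, for the same patients: "attempts should be made to obtain any death information available via public records".

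None of the three asks for proof that a patient is alive, or says what date a search with no result establishes.

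**Analysing survival.** Protocol 10.5.2: "Patients who are alive or lost to follow-up at the time of the analysis will be censored at the last known alive date". SAP 3.2: "In the absence of confirmation of death, survival time will be censored at the last date the patient is known to be alive". Under the SAP sentence a confirmed death is an event whatever its source; otherwise the patient is censored at her last known alive date.

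Protocol 10.5.2 also promises OS sensitivity analyses in the SAP. SAP 5.5.3 lists stratified and unstratified log-rank tests, and nothing that addresses loss to follow-up.

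**The concern.** Take two patients last contacted at month 6. One dies at month 14 and the death is found in records: she contributes 14 months and an event. The other is alive at month 14: she contributes 6 months and no event. Both were unobserved from month 6, yet only the one who died has that time counted.

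Censoring then depends on the outcome, even if loss itself has nothing to do with prognosis. Kaplan-Meier, log-rank and Cox methods all assume that it does not. Survival is understated in any arm with losses. If the arms lose patients at different rates, the hazard ratio moves against the arm that loses more.

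OS is a listed secondary objective. Its curves, medians and hazard ratio will be reported, and the distortion grows with follow-up, as OS becomes more informative.

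**Working it through.** **The plan's own figure.** The documents give no OS sample size, loss rate or record-capture rate. Their one event calculation is for PFS: 4(1.2816 + 0.8416)²/(ln 0.57)² = 18.03/0.3160 = 57.1, rounded up to the stated 58. It reproduces and does not involve OS.

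**Inputs.** From Protocol 10.2: 80 patients, 1:1, 16 months of accrual, 20 months in total. Median OS is assumed to be 24 months, because 10.5.2 says only "The majority of patients are expected to live at least 2 years"; Protocol 1.1 gives a background range of 18-36 months. Assumed: exponential survival, uniform accrual, exponential loss unrelated to prognosis, and the loss and capture rates shown.

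**Mechanism.** The hazard is λ = ln 2/24 = 0.02888 per month. Follow 100 lost patients for the 12 months after loss.
- Deaths: 100(1 − e^(−12λ)) = 100(1 − 0.7071) = 29.3.
- True time at risk: 29.3/0.02888 = 1,014 months.
- Time of the 70.7 survivors, which is dropped: 70.7 × 12 = 849 months.
- Time counted: 1,014 − 849 = about 166 months.
- Apparent hazard after loss: 29.3/166 = 0.177, about six times the true 0.0289.

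If records find only half of the deaths, deaths and counted time both halve. The apparent hazard stays the same but carries less weight, so the bias shrinks without vanishing.

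**Survival curve.** Simulated with 400,000 patients per arm, cut-off at month 36, all deaths found:

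| Lost by 24 months | S(24), true 0.500 | Median, true 24.0 months |
|---|---|---|
| 5% | 0.494 | 23.6 |
| 10% | 0.486 | 23.1 |
| 20% | 0.472 | 22.3 |
| 30% | 0.453 | 21.5 |

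With 20% lost, S(24) falls from 0.397 to 0.370 if the true median is 18 months, and from 0.630 to 0.605 if it is 36. At the month-20 PFS analysis (median 24), S(12) falls from 0.707 to 0.696.

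**Hazard ratio** (Cox, experimental v control):

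| Lost, experimental v control | Cut-off | Deaths found | True HR | HR as written |
|---|---|---|---|---|
| 20% v 20% by 24 months | 36 | 100% | 1.0 | 1.00 |
| 20% v 20% by 24 months | 36 | 100% | 0.70 | 0.705 |
| 20% v 5% by 24 months | 36 | 100% | 1.0 | 1.06 |
| 5% v 20% by 24 months | 36 | 100% | 1.0 | 0.94 |
| 20% v 5% by 24 months | 36 | 50% | 1.0 | 1.03 |
| 20% v 5% per year | 20 | 50-100% | 1.0 | about 1.03-1.08 |
| 20% v 5% per year | 40 | 50-100% | 1.0 | about 1.07-1.13 |

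The per-year rows assume heavier loss: 20% per year is 1 − 0.8² = 36% by 24 months. Month 40 is an assumed later analysis, because no OS analysis date is given.

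**Against sampling error.** Expected deaths by month c are 80[1 − (e^(−λ(c−16)) − e^(−λc))/(16λ)].
- Month 20: 80[1 − (0.8909 − 0.5612)/0.4621] = 22.9, so SE(log HR) ≈ 2/√22.9 = 0.42. Here ln 1.08 = 0.077, or 0.18 SE.
- Month 40: 80[1 − (0.5000 − 0.3150)/0.4621] = 48.0, so SE ≈ 2/√48.0 = 0.29. Here ln 1.13 = 0.122, or 0.42 SE.

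**Alternative rules.** With loss unrelated to prognosis, censoring every lost patient at last contact and following every lost patient to the cut-off both return HR 1.00 (true 1.0) or 0.70 (true 0.70), whatever the losses by arm. They differ when loss precedes death. Let the loss hazard rise 3- to 6-fold in the 3 months before death (month 20, 20% v 5% per year, all deaths found, true HR 1.0):
- Rule as written: 1.08.
- All censored at last contact: 0.94 falling to about 0.84.
- Search with complete records, negatives dated to the cut-off: 1.00.

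If records find only 80% of deaths, dating every negative to the cut-off understates the death rate by up to 6%.

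**The case against.** **The rule may not be asymmetric.** Read alone, Protocol 10.5.2 could censor every lost patient, including one whose death is later found. That would remove the asymmetry, and no sentence says outright that a record-found death counts at its date. The SAP is also headed for a different protocol number and describes a phase 3 trial, which weakens it as support. This stands as a reason to call the text ambiguous. But Protocol 4.4, 6.1 and 6.6 would then collect death dates for no stated use, and SAP 3.2 points to counting them.

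**A search with no result could advance the last known alive date.** That would largely remove the bias where records are complete, but no section says so.

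**Unequal loss is not shown.** A reader might infer that more patients on seribantumab will leave follow-up because of toxicity, and so that OS will be biased against it. The documents do not support this. Protocol 3.1 requires survival follow-up for all patients, 4.4 continues it every 2 months after treatment stops for any reason, and the trial is double-blind. The unequal rates above are illustrations.

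**Size.** The loss and capture rates are assumed, and 6.6 asks for records only where possible. OS is secondary, and 10.5.2 expects too few deaths for a formal test at the PFS analysis. All of this stands.

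**The simple remedy can do harm.** A reader might infer that record-only deaths should not count. That discards known deaths, and when patients drop out shortly before dying it favours the arm with more loss (0.94 to about 0.84 above).

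**Conclusion.** The concern holds as a gap in the OS censoring rule. The plan does not say how a record-found death or a search with no result enters the analysis, and its natural reading censors by outcome. The curves are then too low: about 1-3 percentage points of 24-month survival with 5-20% lost by 24 months, under a 24-month median, independent loss and full capture. A material shift in the hazard ratio needs unequal loss, and the direction follows whichever arm loses more.

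The shift is at most about 0.2 standard errors at month 20 and 0.4 at month 40 in the scenarios examined. It is systematic, so more patients would not remove it. The documents do not support saying that the trial's OS hazard ratio will be biased, or which way. The 58-event PFS analysis does not change. This should be corrected, but it does not threaten the main conclusion.

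**What to change.** In Protocol 10.5.2 and SAP 3.2:

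1. At the OS data cut-off, run one dated record search for every lost patient in both arms, where permitted. Count deaths found up to that date.
2. Where the record source is complete, censor patients with no death record at the date through which it is complete.
3. Where records are incomplete, keep the current rule as primary, stating explicitly that record-found deaths count. Add a sensitivity analysis that censors every lost patient at last contact regardless of later record deaths, and state that it is valid only if loss is unrelated to prognosis.
4. Report loss to follow-up and record-only deaths by arm.

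The cost is wording in two sections, one dated search per lost patient (a search is already planned, without a date) and one extra analysis.

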### 4.1. Inclusion Criteria

To be eligible for participation in the study, patients must meet the following criteria. Patients who are HRG negative do not need to complete screening procedures beyond HRG assessment:

- a) Histologically or cytologically confirmed ER+ and/or PR+ (with staining of  $\geq$  1% cells) breast cancer
- b) Confirmed postmenopausal status due to either surgical/natural menopause or ovarian suppression (initiated at least 28 days prior to Day 1 of Cycle 1) with a gonadotropin-releasing hormone (GnRH) agonist such as goserelin
- c) HER2 negative per ASCO/CAP guidelines
- d) A positive in-situ hybridization (ISH) test for heregulin with a score of  $\geq 1+$ , as determined by centralized testing of unstained tumor tissue
- e) Must have at least one lesion amenable to either core needle biopsy or fine needle aspiration
- f) Progressed following at least one but no more than two prior systemic therapies in the locally advanced or metastatic disease setting
  - Received prior CDK inhibitor based therapy for locally advanced or metastatic disease
- g) Documented progression of locally advanced or metastatic disease as defined by RECIST v1.1. *Exception:* patients with bone-only metastatic disease are eligible if they have at least 2 lytic lesions visible on a CT or MRI and have documented disease progression on prior therapy based on the appearance of new lesions.
  - Patients with bone-only lesions who have received radiation to those lesions must have documented progression following radiation therapy.
- h) Able to understand and sign an informed consent (or have a legal representative who is able to do so)
- i) ECOG Performance Score (PS) of 0 or 1
- j) Adequate bone marrow reserves as evidenced by:
  - ANC  $> 1500/\mu l$
  - Platelet count  $> 100,000/\mu l$ ; and
  - Hemoglobin > 9 g/dL
- k) Adequate hepatic function as evidenced by:
  - Serum total bilirubin  $\leq 1.5$  x ULN except for patients with Morbus Gilbert
  - Aspartate aminotransferase (AST), Alanine aminotransferase (ALT) and Alkaline Phosphatase  $\leq 2.5 \text{ x ULN}$  ( $\leq 5 \text{ x ULN}$  is acceptable if liver metastases are present,

and  $\leq$  5 x ULN of Alkaline Phosphatase is acceptable if bone metastases are present)

- 1) Adequate renal function as evidenced by a serum creatinine  $\leq 1.5 \text{ x ULN}$
- m) Recovered from clinically significant effects of any prior surgery, radiotherapy, or other antineoplastic therapy.

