## 3.5 **Objective Response Rate**

Objective Response Rate (ORR) will be derived using the investigator-assessed tumor assessment data. Best Overall Response (BOR) is recorded from randomization until documented disease progression or death. ORR is defined as the proportion of patients with a BOR characterized as either a Complete Response (CR) or Partial Response (PR) as defined according to RECISTv1.1 guidelines relative to the total number of evaluable patients. Per RECISTv1.1 guidelines, patients with documented PR or CR will not need confirmatory tumor assessments to document response. Patients without baseline or post-baseline tumor assessments will be considered non-evaluable for this analysis. The following table describes the responder/non-responders for this analysis.

Table 3.5	ORR Determination
-----------	--------------------------

Criteria	Responder/Non- responder
No Baseline tumor assessment	Not Evaluable
No Post-baseline tumor assessment AND were treatment failure prior to BOR determination due to disease progression, symptomatic deterioration, toxicity, death, or new anticancer treatment	Non-Responder
BOR: Partial Response, Complete Response	Responder
AND were not treatment failure prior to BOR determination due to disease progression, symptomatic deterioration, toxicity, death, or new anticancer treatment	
BOR: Stable Disease, Progressive Disease, Not Evaluable/Indeterminate	Non-responder

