# NOTE: Shortest axis is used as the diameter for malignant lymph nodes, longest axis for all other measurable lesions.

Non-measurable disease - Defined as lesions too small to be considered measurable (including nodes with short axis between 10 and 14.9 mm) and truly non-measurable disease such as pleural or pericardial effusions, ascites, inflammatory breast disease, leptomeningeal disease, lymphangitic involvement of skin or lung, clinical lesions that cannot be accurately measured with calipers, abdominal masses identified by physical exam that are not measurable by reproducible imaging techniques.

- Bone disease: Not measurable with the exception of soft tissue components that can be evaluated by CT or MRI and meet the definition of measurability at baseline.
- Previous local treatment: A previously irradiated lesion (or lesion subjected to other local treatment) is nonmeasurable unless it has progressed since completion of treatment.

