#### Non-target disease

- CR: Disappearance of all non-target lesions and normalization of tumor marker levels. All lymph nodes must be 'normal' in size (<10 mm short axis).
- Non-CR/Non-PD: Persistence of any non-target lesions and/or tumor marker level above the normal limits.
- PD: Unequivocal progression of pre-existing lesions. Generally the overall tumor burden must increase sufficiently to merit discontinuation of therapy. In the presence of SD or PR in target disease, progression due to unequivocal increase in non-target disease should be rare.
- Not Evaluable: Progression has not been determined and one or more non-target sites were not assessed or assessment methods were inconsistent with those used at baseline.

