## Table 1. Objective Response Status at each Evaluation

Target Lesions	Non-target Lesions	New Lesions	Objective Status
CR	CR	No	CR
CR	Non-CR/Non-PD	No	PR
CR	NE, or Missing	No	PR
PR	Non-CR/Non-PD, NE, or Missing	No	PR
SD	Non-CR/Non-PD, NE, or Missing	No	SD
NE or Missing	Non-PD	No	NE
PD	Any	Yes or No	PD
Any	PD	Yes or No	PD
Any	Any	Yes	PD

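### SAP response rules give bone-only patients without a measurable soft tissue component no route to CR or PR, yet keep them in the ORR denominator

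*Protocol*

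**What the plan says.** **Eligibility.** Protocol 4.1(g) states that "patients with bone-only metastatic disease are eligible if they have at least 2 lytic lesions visible" on CT or MRI. No soft tissue component is required. Protocol 5.1 makes bone-only disease a randomization stratum.

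**Denominator.** Protocol 10.5.2 takes responders "relative to the total number of evaluable patients" and leaves evaluable undefined. SAP 3.5 gives one reason for exclusion: "Patients without baseline or post-baseline tumor assessments will be considered non-evaluable for this analysis". Lack of measurable disease is not a reason.

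**Measurability.** The SAP appendix says "Bone disease: Not measurable with the exception of soft tissue components" that meet its size rules, and assigns all non-measurable disease to the non-target category.

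**Scoring.** The appendix defines a non-target CR as "Disappearance of all non-target lesions and normalization of tumor marker levels". In appendix Table 1, however, an overall CR or PR always starts from a target response of CR or PR. The row for patients without a target response and without progression reads "NE or Missing Non-PD No NE". SAP Table 3.5 then lists "BOR: Stable Disease, Progressive Disease, Not Evaluable/Indeterminate" as non-responder.

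**Analysis.** Protocol 10.5.2 plans a CMH test stratified by the stratification factors and an unstratified chi-square. SAP 5.5.3 adds a relative risk and a normal-approximation risk difference. The strata in SAP 3.7 are prior chemotherapy, backbone and region. Bone-only disease is not among them.

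**The concern.** ORR is a named secondary endpoint. Read together, these rules place in its denominator a group in whom response cannot be recorded, whatever happens to their disease. The reported rate in each arm and the risk difference then depend on how many such patients are enrolled as well as on drug activity. They become harder to compare with rates from measurable disease. The waterfall plots of percentage change in SAP 5.5.3 need a target-lesion sum, so they would rest on a different set of patients from the ORR beside them.

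**Working it through.** **Figures in the plan.** The documents state no ORR, no ORR difference and no bone-only share, so there is no ORR figure to reproduce. The one design calculation is 58 PFS events (HR 0.57, 80% power, one-sided 0.10, 1:1). It reproduces with the Schoenfeld formula but is not an input here. The only design input used below is 80 randomized 1:1, or 40 per arm.

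**Following one patient through the rules**
1. She has two lytic lesions and no soft tissue component: eligible (Protocol 4.1(g)).
2. Her disease is non-measurable, so she has no target lesion (SAP appendix).
3. At each visit without progression, no Table 1 row starting from target CR, PR or SD applies. The row that fits gives NE. Non-target CR does not help, because it leads to overall CR only together with target CR.
4. Her best response is NE or PD. Both are non-responder in Table 3.5.
5. She has baseline and post-baseline assessments, so SAP 3.5 does not remove her.

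**Size.** Let b be the share of each arm made up of such patients (assumed), and p the response rate in measurable disease (assumed). Then

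reported ORR = (1-b) × p

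reported difference = (1-b) × (p1 - p0), if b is equal in both arms.

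| b | 30% v 10% becomes | Difference (20 points) | 20% v 10% becomes | Difference (10 points) |
|---|---|---|---|---|
| 10% | 27% v 9% | 18 | 18% v 9% | 9 |
| 20% | 24% v 8% | 16 | 16% v 8% | 8 |
| 30% | 21% v 7% | 14 | 14% v 7% | 7 |

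The loss is relative. At b = 20%, a 20-point difference loses 4 points, not 20.

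**Soft tissue components.** If a quarter or a half of a 20% bone-only group has a measurable component and responds like the other patients, the relative loss is 20% × 0.75 = 15% or 20% × 0.5 = 10%.

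**What does not move (equal shares).** The relative risk stays at 3.0 (or 2.0), because (1-b) cancels. For 30% v 10% at b = 20%, using expected counts with 40 per arm:
- The CMH statistic stratified on bone-only disease is 3.94 with or without the bone-only stratum, since a stratum with no responders contributes nothing.
- The unstratified chi-square in measurable disease is 0.20² / (0.20 × 0.80 × 2/32) = 4.00.
- The unstratified chi-square in all patients is 0.16² / (0.16 × 0.84 × 2/40) = 3.81.

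**Unequal shares.** With 30% v 10% and shares of 15% (seribantumab) v 25% (control), the difference is 25.5 - 7.5 = 18 points and the relative risk is 3.4. With shares reversed, it is 22.5 - 8.5 = 14 points and 2.65. Stratified randomization should keep the shares close.

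**The case against.** **Table 1 may not be meant for these patients.** It has no row headed for patients without target lesions at baseline. The SAP's definition of a not-evaluable target response describes lesions that exist but were not properly assessed, and both documents defer to RECIST v1.1. SAP 5.4.3 even plans to count patients with non-target lesions only. This has force as to intent. But if the NE row is not meant for them, they have no non-progression row at all, and on neither reading does the table offer a response. The NE reading could also expose them to the PFS censoring rule for consecutive not-evaluable assessments (SAP 3.1), which is a further reason to state the scoring.

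**The SAP was written for another design.** It names protocol 02-03-10, a phase 3 trial with exemestane or fulvestrant. That is correct. The defect lies in SAP 3.5 and appendix Table 1; Protocol 10.5.2 only leaves the gap open. It is still the only SAP supplied.

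**An ORR over all assessed patients is a legitimate, conservative choice.** This also stands in part. The reported rate is low only relative to ORR in measurable disease, and the documents do not say which population ORR should describe. The choice does not, however, justify a rule that codes complete disappearance of disease as not evaluable.

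**Treatment inference is hardly touched.** This is right for the relative risk and for the protocol's CMH test. It does not cover the arm-level rates, the risk difference, or a CMH test run on the SAP's current strata, which would not isolate these patients.

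**Conclusion.** The point holds for bone-only patients without a measurable soft tissue component. The written rules give them no route to CR or PR and keep them in the denominator. Reported ORR and the unstratified risk difference are then (1-b) times the values in measurable disease: 18, 16 or 14 points instead of 20 at b = 10%, 20% or 30%. Both b and the response rates are assumptions, and the scaling of the difference needs equal shares in the two arms.

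A reader might infer more, and the documents do not support it:
- Bone-only patients can never respond. The SAP appendix allows a bone lesion with a measurable soft tissue component to be a target lesion.
- ORR is understated by the bone-only share. The loss is a proportion, not percentage points; it is smaller if some patients have soft tissue components; and no share is given.
- The treatment comparison is biased throughout. With equal shares, the relative risk and the CMH test stratified on bone-only disease are unchanged.

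This is a modest defect in a secondary endpoint. It does not affect the sample size calculation.

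**What to change.** When the SAP is aligned to this protocol:
1. Define *evaluable* for ORR, in Protocol 10.5.2 and SAP 3.5, as measurable disease at baseline. Report the all-randomised rate as a supportive line.
2. Add rows to appendix Table 1 for non-target-only disease, so that non-target CR and non-CR/non-PD have their own outcomes and are not coded NE.
3. Stratify the CMH test for ORR by bone-only disease, as the protocol's factors require.
4. State that the percentage-change waterfall plots use the measurable-disease set.

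**Cost.** This is SAP wording plus one protocol definition. The ORR set falls from 40 per arm to 36, 32 or 28 at b = 10%, 20% or 30%, and the interval widens. At b = 20% with 30% v 10%, the 95% half-width is 1.96 × √[(0.21 + 0.09)/32] = 19.0 points around 20. In all patients it is 1.96 × √[(0.1824 + 0.0736)/40] = 15.7 points around 16. Relative to the estimate, little precision is lost.
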